## 4.4 Heavy Lozenge Use (HLU) Population

The heavy lozenge use population will be a subset of the mITT population and will consist of subjects who use on average 15 or more lozenges per day (irrespective of completion of the study).

### 4.5 Concomitant Smoker (CS) Population

The concomitant smoker population will be a subset of the mITT population and will consist of subjects who either admit smoking during the study or who have a CO > 10 ppm at any study day excluding Day 0 or Day 24 that cannot otherwise be explained.

### 5 ASSESSMENT AND STUDY ENDPOINTS

## 5.1 Oral Safety Assessment

Oral examinations will be conducted using a 20 Item Oral Mucositis Index (OMI-20), a validated scale developed to measure several indications of oral mucositis. Assessors will be licensed dental professionals (dental hygienists or dentists). These selected dental professionals will be trained in the assessment protocol and the OMI-20 by a board-certified oral medicine professional. Prior to initiation of study visits, the selected dental professionals will be trained onsite in the assessment protocol and the OMI-20 test. An assessment will be conducted to ensure consistent evaluation among the dental professionals that will partake in the study. All assessors will be blinded to the study treatment the subject has been randomized to receive. OMI-20 will be assessed on Days 0, 3, 7, 14, 21 and Day 24 (post dose) visits.

## 5.2 Primary Endpoint

OMI-20 Total score change from baseline (Day 0) at each study visit (Days 3, 7, 14 and 21) in the Modified-Intent-to-Treat (mITT) population.

17-May-2017 Final Version 1.0 Page 12 of 53

Sponsor Protocol No. 2016-NBTL-S-005

## 5.3 Secondary Endpoints

- OMI-20 Total score change from baseline (Day 0) at each study visit (Days 3, 7, 14 and 21) in PP population, heavy lozenge use population and concomitant smoker population.
- OMI-20 Erythema subscore change from baseline at each study visit (Days 3, 7, 14 and 21) in all populations.
- OMI-20 Ulcer subscore change from baseline at each study visit (Days 3, 7, 14 and 21) in all populations.

## 5.4 Safety Endpoints

- Clinical laboratory assessments (clinical chemistry; hematology; serology; urinalysis)
- Vital signs
- 12-lead Electrocardiogram (ECG)
- Analysis of biopsied materials (if any) and adverse events

## 5.5 Other Safety Endpoints

- OMI-20 Total score Day 24 versus Day 21
- OMI-20 Erythema score Day 24 versus Day 21
- OMI-20 Ulcer score Day 24 versus Day 21
- Safety endpoints Day 24 versus Day 21

### **6 STATISTICAL METHODOLOGY**

## **6.1 Summary Statistics**

Subject disposition will be summarized for all the randomized subjects. The primary endpoints will be summarized for mITT population. The secondary endpoints will be summarized for mITT population, PP population, HLU population and CS population. The safety endpoints and baseline characteristics will be summarized only for the mITT population.

The standard summary statistics that will be calculated for quantitative and qualitative variables are:

Quantitative: number of subjects, mean, median, standard deviation (SD), minimum and maximum of the raw data

Qualitative: number of subjects, number of missing data (if not zero), absolute and relative frequencies per class

17-May-2017 Final Version 1.0 Page 13 of 53

Sponsor Protocol No. 2016-NBTL-S-005

### 6.2 Reporting Precision

Summary statistics will be presented to the following degree of precision:

Statistics	Degree of Precision
Mean (of all kinds), Median,	One more decimal place than the raw data
Standard deviation	Two more decimal places than the raw data
Minimum, Maximum	The same number of decimal places as the raw data
Percent	One decimal place

### 6.3 Commonly Used Algorithms

#### 6.3.1 Duration of Adverse Events

When adverse events (AEs) have incomplete start dates and times, no imputation will be performed. Duration will be calculated for AEs that resolve as the difference between the resolution date and time and onset date and time and will be expressed in days, hours and minutes. If either time is missing, duration will be expressed in days. Duration will only be calculated when both dates are complete.

## 6.4 Data Handling Rules

The following section describes the rules for handling data, including the definitions of derived variables and handling missing data.

#### 6.4.1 Derived Variables

Age is calculated in years after rounding down as follows:
 Year of age = (Date [in days format] informed consent signed - Date [in days format] of birth) / 365.25

#### 6.4.2 Missing Data

Any missing values for the study endpoints will not be replaced and the observed data will be used for the endpoint analysis. No data interpolation or extrapolation will be carried out if there is missing data.

17-May-2017 Final Version 1.0 Page 14 of 53

Sponsor Protocol No. 2016-NBTL-S-005

### 6.5 Level of Significance

No formal comparisons between groups will be conducted. No inferential statistics will be output. Therefore, no level of significance will be assigned.

## 6.6 Interim Analysis

No interim analysis is planned for this study.

#### 7 STATISTICAL ANALYSES

### 7.1 Subject Disposition and Withdrawals

The following frequencies (number and percent) will be displayed by treatment group and overall for all the randomized subjects:

- Subjects in the Randomized Population (number only)
- Subjects in the Modified Intent-to-Treat Population (number only)
- Subjects in the Per-Protocol Population (number only)
- Subjects in the Heavy Lozenge Use Population (number only)
- Subjects in the Concomitant Smoker Population (number only)
- Subjects who completed the study (number and percent)
- Subjects who discontinued early, as well as reasons for subject discontinuation (number and percent)

The denominators for the percent calculations will be the number of subjects in the Randomized population per treatment or overall.

Subjects' completion/discontinuation status will be listed by treatment group and will include subject identifier, date of enrollment, date of completion/early discontinuation, date of last contact and, for those who discontinued early, the specific reason for discontinuation.

All deviations related to study inclusion or exclusion criteria, conduct of the trial, subject compliance or subject concomitant smoking will be listed. The justification of major/minor on protocol deviations may be determined among the Principal Investigator and Biostatistician from Inflamax Research, and the Sponsor.

17-May-2017 Final Version 1.0 Page 15 of 53

Sponsor Protocol No. 2016-NBTL-S-005

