## 4.3 Per-Protocol (PP) Population

The per-protocol population will be a subset of the mITT population and will consist of subjects who complete the study without any major protocol deviations, as determined by clinical review. Major protocol deviations include:

- CO levels exceeding 10 ppm at one or more study day visit (CO is expected to be > 10 ppm on Day 0)
- Use of < 9 or > 20 lozenges/day on more than 2 study days

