## 7.8 Analysis Prior to Study Completion

An early statistical analysis of data of administrative type is planned for this study following completion of the 60th randomized subject and prior to the completion of full study with 100 randomized subjects and hard lock of the clinical database. This statistical analysis provides with only descriptive summaries and without any confirmatory type of analysis using statistical significance. This will provide an initial evaluation of selected study results and an assessment of adequacy of the result outputs for the final study report.

The study is blinded only to the extent that the dental hygienist evaluating the oral health of subjects does not know to which treatment group the subjects have been assigned. Otherwise the study could be considered an open label study as the subjects, investigators, and study staff are not blinded to the treatment. The individual dental hygienist evaluating the oral health of subjects will not be informed of the results of this pre-planned analysis prior to the completion of the full study analysis. The study will continue to recruit and randomize beyond 60 subjects until the protocol specified 100 randomized subjects are evaluated. Also, the results of the completed study will be presented in the final report, only descriptively.

17-May-2017 Final Version 1.0 Page 20 of 53

Sponsor Protocol No. 2016-NBTL-S-005

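### Deviation grading and the judgement that a high CO reading is explained are neither masked to arm and OMI-20 score nor fixed before scores are seen, so part of PP and CS membership is open to choice

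*SAP*

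**What the plan says.** Two judgements feed the analysis sets.

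- **Deviation severity, which decides PP.** SAP 4.3 defines the PP set as "subjects who complete the study without any major protocol deviations, as determined by clinical review". It names two major deviations, both numeric: CO above 10 ppm at one or more study visits (Day 0 aside), and fewer than 9 or more than 20 lozenges a day on more than 2 study days. The SAP does not say that the list is complete, and the protocol synopsis presents the same two items as examples. On who decides, SAP 7.1 says: "The justification of major/minor on protocol deviations may be determined among the Principal Investigator and Biostatistician from Inflamax Research, and the Sponsor".
- **Whether a CO reading is explained, which decides part of CS.** SAP 4.5 admits a subject who reports smoking, or who has CO above 10 ppm on a study day other than Day 0 or Day 24 "that cannot otherwise be explained". It gives no decision-maker and no list of acceptable explanations.

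On masking, SAP 7.8 says that "the subjects, investigators, and study staff are not blinded to the treatment" and that only the dental hygienist who does the oral evaluation is unaware of the arm. SAP 3.2 masks the oral assessor alone. Its separate eCRF keeps lozenge data from the assessor; it does not keep OMI-20 scores or arm from those who decide membership. SAP 7.8 also plans descriptive summaries after the 60th randomized subject completes, and withholds them only from the hygienist.

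**The concern.** Blinded OMI-20 scoring is the trial's one masking safeguard. It protects each score but not the choice of whose scores enter a table. If someone who knows the arm, and can see the score, grades a deviation or accepts an explanation for a CO reading, a subject can move into or out of PP or CS for reasons connected with the outcome. No formal comparison is planned, so readers will compare arm means by eye, in a sponsor's comparison of its own product with a competitor's. The PP and CS tables would then be open to a criticism that the plan could have prevented.

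**Working it through.** **1. Figures in the plan.** There is none to reproduce. SAP 3.3 gives 50 subjects per arm without a calculation, SAP 6.5 sets no significance level, and no SD for OMI-20 change or expected size for PP or CS is stated. The check is therefore of the text, with arithmetic only to show scale.

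**2. Where judgement enters.**

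| Route | Rule | Judgement needed? |
|---|---|---|
| Out of PP: CO > 10 ppm | Numeric, no exception (SAP 4.3) | No |
| Out of PP: lozenge use | Numeric; SAP 7.4 makes it a major violation | No |
| Out of PP: any other deviation | Major/minor grading (SAP 4.3, 7.1) | Yes |
| Into CS: admitted smoking | Self-report (SAP 4.5) | No |
| Into CS: CO > 10 ppm, smoking not admitted | Unless explained (SAP 4.5) | Yes |

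**3. Who judges, and what they know.** For deviation grading, three parties are named. The investigator is expressly unblinded by SAP 7.8. The CRO biostatistician and the sponsor are not named there, so their knowledge of arm is an inference from the hygienist being the only masked party. For CO explanations no one is named. The shells for the deviation listing (16.2.2) and the CO listing (16.2.5.2) both have treatment as their first column, and no masked version is planned in the available text.

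**4. Tables reached.** SAP section 8 has 3 scores × 4 populations = 12 change tables. PP and CS account for 3 × 2 = 6. SAP 7.7.6 also presents the Day 21 to Day 24 differences in the subpopulations. The mITT set (randomized and used at least one lozenge) needs neither judgement.

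**5. Scale in score points, on assumed inputs.** If an arm of n subjects has mean change M, and k subjects with change x are removed, the new mean is (nM − kx)/(n − k). Assume M = 1.0 and x = +6:

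- n = 25, k = 1: (25 − 6)/24 = 0.79
- n = 25, k = 2: (25 − 12)/23 = 0.57
- n = 15, k = 1: (15 − 6)/14 = 0.64
- n = 15, k = 2: (15 − 12)/13 = 0.23

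**6. Scale in SD units, by simulation.** Assume normal change scores and m discretionary subjects among n in one arm, with the worst-scoring half of those m removed. The shift in that arm's mean is set against the standard error of a between-arm difference with n per arm, SE = √(2/n):

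| n per arm | Remove 2 of 4 | Remove 5 of 10 | SE | Shift / SE |
|---|---|---|---|---|
| 50 | −0.028 | −0.082 | 0.200 | 0.14 to 0.41 |
| 30 | −0.047 | −0.148 | 0.258 | 0.18 to 0.57 |
| 15 | −0.102 | −0.370 | 0.365 | 0.28 to 1.01 |

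This assumes deliberate selection on known scores, all in one arm. Membership decisions unrelated to score would give no shift on average.

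**The case against.** The case on the other side is substantial.

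- **Most membership is rule-based.** Both named PP exclusions are numeric and leave no room for a minor grade, and admitted smoking enters CS automatically. This stands, and it is why the point is confined to the two judgement rows in the table.
- **Knowledge of arm is partly inferred.** A reader might infer that everyone who decides knows the treatment. The documents establish this only for the investigator, and no decision-maker is named for CO explanations. What stands is that no masking is stated.
- **Blinded scoring is intact.** A reader might infer that its protection is lost in the PP and CS tables. It is not: the scores remain blinded, and only the selection of subjects is exposed.
- **The two CO rules differ.** A subject with an explained high reading who does not admit smoking falls in neither PP nor CS, and a reader might call that a contradiction. The documents do not support this. Each set is defined only as a subset of mITT, nothing makes them complementary, and the protocol has the same two rules. Extending the explained exception to PP would add discretion where there is none now.
- **Listings allow checking.** Deviations, CO, lozenge use and OMI-20 are listed by subject, so the numeric exclusions can be verified. This helps with the rules but not with the judgements, since neither the deviation shell nor the CO shell has a field for the reason behind a decision.
- **Coverage.** The protocol text available stops at the list of abbreviations, and the data management plan cited in SAP 1 is not available. Masking could be described there.

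**Conclusion.** The point holds as a gap in how the secondary sets are formed. Major/minor grading of unlisted deviations, and acceptance of CO explanations in subjects who do not admit smoking, are not masked to arm or OMI-20 score in the available text and are not required before scores are seen. At least one named participant in the grading knows the arm.

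The reach is the secondary descriptive PP and CS tables and the recovery summaries in those sets. The primary mITT summary is untouched, and with no testing there is no error rate to affect. The size cannot be derived from the documents. On the assumptions shown it is small in a large set and can reach about one standard error of the between-arm difference with 15 per arm, which makes a small CS set the more sensitive. The documents show an opportunity for outcome-related classification. They do not show an intention, or that it happened.

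The change is worth making because it is cheap and alters the method in a useful way. It does not put the main result in doubt.

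**What to change.** In SAP 4.3, 4.5 and 7.1, state that:

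1. Major/minor grading and CO-explanation decisions are made from a listing that omits treatment, OMI-20 and adverse event data.
2. The people who make each decision are named by role. The investigator supplies the facts of each case. Whether the investigator also votes is for the sponsor to settle, bearing in mind that a listing cannot mask someone who already knows the arm.
3. Each decision is recorded with its reason, signed, and frozen before any by-arm OMI-20 output is run. For the first 60 subjects this means before the SAP 7.8 analysis; for the rest, before database lock.

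Leave the numeric PP rule for CO unchanged, so that it stays free of judgement and in line with the protocol.

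The cost is one masked listing format and two short review and sign-off steps, one before the 60-subject output and one before lock. No new data are needed and the primary analysis does not change. The drawback is the short delay that each review adds.

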### 7.2 Baseline Characteristics

Demographics (age, sex, race, ethnicity, weight, height and BMI) will be summarized using descriptive statistics (number of subjects, mean, standard deviation, minimum, median and maximum for quantitative variables, and number of subjects and percent of subjects for qualitative variables) by treatment group and overall for the mITT population. No formal statistical comparison between treatment groups will be performed. Together with the informed consent date, the above information will be listed by treatment groups for the randomized subjects.

Other baseline characteristics will be listed by treatment group for all subjects:

- Medical/medication history
- History of Tobacco/nicotine product use/consumption and smoking/vaping habits
- Pregnancies (female only)
- Urine drug screen and alcohol breathalyzer test

The history of tobacco/nicotine production use/consumption and smoking/vaping habits will be listed as treatment, subject, substance name, start date of use, end date of use, ongoing use, frequency of use, amount used (amount/unit/frequency).. A summary table will be produced by treatment for the duration of substance use and average amount. The summary statistics will also report the number of subjects who reported using the product at each frequency level (less than 20 cigarettes per day, 20 – 29 per day, and more than 30 per day) within treatment group and overall.

#### 7.3 Concomitant Medication

The use of concomitant medications will be requested in the ePDAT® system, and subjects will be able to indicate whether any concomitant medication was used during the study. The full description of the concomitant medication usage will be recorded in the take-home journals provided to the subjects, indicating the following information (as possible): Name of drug, Reason for use, Frequency of use, Route of administration, Dose, and Start date and Stop date (where applicable). The above information will listed by treatment. No summary table will be output.

## 7.4 Medication Administration and Treatment Compliance

Subjects will be instructed to self-administer 9-20 lozenges per day and record lozenge use through Inflamax's ePDAT take-home tablet once daily. Number of used lozenges since last visit will be calculated as deduction of the dispensed lozenge number of last visit from the

17-May-2017 Final Version 1.0 Page 16 of 53

Sponsor Protocol No. 2016-NBTL-S-005

returned lozenge number of this visit. Average number of lozenges used per day will be also calculated as dividing total number of used lozenges by total number of treatment days.

Treatment compliance will be determined by Breath Carbon Monoxide (CO) and average number of lozenges.

Breath carbon monoxide (CO) levels will be presented by subject for each visit and will be used to identify concurrent smokers. Based on level of CO, subjects will be divided as compliant subjects (CO<=10 ppm at all study day visits) and non-compliant subjects (CO>10 ppm at any study day visit). Breath carbon monoxide (CO) levels will be listed by treatment, together with visit and date. In the listing, non-compliance will be flagged. For those who comply with the requirements, CO level will be summarized with descriptive statistics (number, mean, SD, minimum, median and maximum) by treatment and visit. The number of subjects and percentage will be calculated based on whether the CO level is higher or lower than 10 ppm.

Number of lozenges will also be used to determine compliance. Lozenge use of less than 9 or more than 20 for more than 2 study days will be treated as a major violation of compliance and qualifies subjects as non-compliant.

The average number of used lozenges will be summarized with descriptive statistics (n, mean, SD, minimum, median and maximum) by treatment for the mITT population and subpopulations. The number of subjects and percentage will also be calculated based on compliance.

Compliance or non-compliance will be tabulated by treatment with frequency and percentage using the mITT population.

Medication administration will be listed by treatment, including subject number, visit, visit date, the number of dispensed lozenges, the number of returned lozenges, the number of used lozenges and average number of lozenges used per day. Non-compliance on specific day(s) will be flagged, and total number of non-compliant days will be listed.

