## 4.2 Modified Intent-to-Treat (mITT) Population

The mITT population will include all subjects who were randomized and used at least 1 lozenge. This will be the main population for analysis.

17-May-2017 Final Version 1.0 Page 11 of 53

Sponsor Protocol No. 2016-NBTL-S-005

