**Table 14.3.6.2 Summary of Study Drug Administration** 

		_	Treatment	
opulation		Statistics	Nicotine Polacrilex	Nicotine Bitartrate
Т	mITT Average number of used lozenges per day	n	xx	xx
		Mean ± SD	$xx.x \pm x.xx$	$xx.x \pm x.xx$
		Median	XX.X	XX.X
		Min, Max	xx, xx	xx, xx
	Number of non-compliance days>2 or not	n (%)		
	Yes		xx (xx.x%)	xx (xx.x%)
	No		xx (xx.x%)	xx (xx.x%)
5				
.U				

Data Source: Listing 16.2.5.2

17-May-2017 Final Version 1.0 Page 34 of 53

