### **Listing 16.2.5.1 Study Drug Administration**

Treatment	Subject	Visit	Dispense/ Administration Date	Number of Dispensed	Number of Returned	Number of Daily Use	Compliance Flag*	Number of Non-Compliance Days
Nicotine Polacrilex	xxxx	Day 0	DDMONYYYY	xx				
		Day 1	DDMONYYYY			XX	Yes	
		Day 7	DDMONYYYY	xx	xx	xx	No	
		Day 21	DDMONYYYY			xx	Yes	
		Day 24	DDMONYYYY		XX			xx
	xxxx	Day 0						

Note: Drug dispense happens on Day 0, 7 and 14; Drug return happens on Day 7, 14 and 24. \*Compliance will be flagged 'No' for daily lozenge use fewer than 9 or more than 20.

17-May-2017 Final Version 1.0 Page 48 of 53

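### SAP Section 7.4 states the lozenge-use count in reverse and ties it to the wrong visit, so the average per day is not true use if the text is followed as written

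*SAP*

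**What the plan says.** SAP Section 7.4 gives the count in one sentence that runs across a page break. The first part is "Number of used lozenges since last visit will be calculated as deduction of the dispensed lozenge number of last visit from the" and the second is "returned lozenge number of this visit. Average number of lozenges used per day will be also calculated". The average is the total of these counts divided by the number of treatment days. Neither document gives the formula anywhere else; the protocol synopsis only says that average daily use will be tabulated.

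The result is used as follows:

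- **Table.** Section 7.4 says that "The average number of used lozenges will be summarized with descriptive statistics" by treatment, for the mITT population and the subpopulations. The matching row in Table 14.3.6.2 is "Average number of used lozenges per day".
- **Listing.** Section 7.4 asks for "the number of returned lozenges, the number of used lozenges and average number of lozenges used per day".
- **Compliance.** Section 7.4 names breath carbon monoxide and average lozenge use as the basis for treatment compliance. It then sets a separate day-count rule: fewer than 9 or more than 20 lozenges on more than 2 study days.

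On timing, Section 2.4 and Table 1 put dispensing at Days 0, 7 and 14, with visits at Days 0, 3, 7, 14, 21 and 24. The note to Listing 16.2.5.1 puts returns at Days 7, 14 and 24.

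**The concern.** To deduct one number from another is to subtract the first from the second. The sentence deducts the number dispensed from the number returned. A subject cannot return more than was dispensed, so with returns matched to dispensing the count is zero or negative.

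The reference to the last visit is a second fault. The visit before the Day 7 return is Day 3, and the visit before the Day 24 return is Day 21. No lozenges are dispensed at either. Only the Day 14 return follows directly on a dispensing visit (Day 7).

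At stake is the description of exposure in a study that compares oral mucosal effects of two lozenges. A reader would set the OMI-20 results beside the average daily use in each group.

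**Working it through.** The documents give no figure to reproduce, so the check applies the written rule to known true use.

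**Inputs**
- Instructed use of 9 to 20 lozenges per day (Section 7.4), and the cut-off of 15 per day for heavy use (Section 4.4). True use u is set to 9, 15 and 20.
- Three dispensing periods, taken as 7 days of use each, 21 days in all.
- Daily Packs of 20 (Section 2.4). Packs per dispensing are not stated. Assumption: 7 packs, so D = 140 dispensed per period.
- Returned per period: r = D - 7u, which gives 77, 35 and 0.

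**Reading A: each return matched to its own dispensing**

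As written, the average is 3 × (r - D) / 21 = 3 × (-7u) / 21 = -u.

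| True use/day | Returned | Count per period | Average/day |
|---|---|---|---|
| 9 | 77 | 77 - 140 = -63 | -9 |
| 15 | 35 | 35 - 140 = -105 | -15 |
| 20 | 0 | 0 - 140 = -140 | -20 |

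D cancels, so the kit size does not matter: with D = 200 the returns are 137, 95 and 60 and the averages are the same. The mITT population is "all subjects who were randomized and used at least 1 lozenge", so with all returns recorded every subject's average is below zero.

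In Table 14.3.6.2 the mean and median change sign, the SD is unchanged, and minimum and maximum trade places. For example, true averages of 9, 12, 15, 18 and 20 have mean 14.8, median 15, SD 4.44 and range 9 to 20. As written they print as mean -14.8, median -15, SD 4.44 and range -20 to -9.

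**Reading B: last visit taken strictly, counts made at the three return visits**

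Day 7 is r - 0, Day 14 is r - D, and Day 24 is r - 0. The average is (3r - D) / 21.

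| True use/day | Day 7 | Day 14 | Day 24 | Average/day |
|---|---|---|---|---|
| 9 | 77 | -63 | 77 | 91/21 = 4.3 |
| 15 | 35 | -105 | 35 | -35/21 = -1.7 |
| 20 | 0 | -140 | 0 | -140/21 = -6.7 |

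Putting r = D - 7u into the formula gives 2D/21 - u. The result now depends on the kit size and falls as true use rises. It equals u only by coincidence, at u = D/21 (6.7 for D = 140).

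If counts are also made at Days 3 and 21 with zero returned, each adds 0 - 140. The total is then 3r - 420 = -21u, so the average is again -u. The visit counts are still not use: at 9 per day, Day 3 shows -140 and Day 7 shows +77.

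**Would reversing the order alone be enough?** Under Reading A it would: 140 - 77 = 63, or 9 per day, and likewise 15 and 20. Under Reading B it would give -4.3, 1.7 and 6.7. The visit reference has to be corrected as well.

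**The case against.** The strongest reply is that this is a slip of wording. A number of lozenges used cannot be negative, the 9 to 20 range and the cut-off of 15 are positive, and a programmer would see the problem at the first output. That stands, and it is why the point is minor. It does not make the written rule right. Section 1 commits the final analysis to the SAP and requires departures to be documented, so the rule should be corrected in the text and not silently in the program.

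A second reply is that Reading A takes the subtraction literally but the visit reference charitably. That is fair. The clean change of sign holds only under matching, and a reader should not infer that every output is sure to appear with the sign reversed. Reading B still does not recover true use.

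Third, the effect on the listing rests on the Section 7.4 text. The shell of Listing 16.2.5.1 has columns for dispensed, returned and "Number of Daily Use", but none for use since the last visit or for the average. The daily column has a Day 1 row that a between-visit count could not fill, so it appears to come from the daily tablet records. Section 8 allows shells to change, so the effect is possible but not shown in the shell.

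Three stronger readings are tempting:

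- **An empty Heavy Lozenge Use population.** Under Reading A nobody would reach 15 per day. But Section 4.4 does not say that membership uses this count, and daily tablet records also exist. The unnamed source is a separate matter.
- **Compliance failing for everyone.** Section 7.4 names the average as a basis for compliance but gives it no threshold. The rule that has thresholds counts days and needs daily records.
- **A rule for missing returns already set by Section 6.4.2.** That section covers missing values of study endpoints. It sets no denominator for lozenge counts, and this point does not need one.

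**Conclusion.** The point holds as a minor error in a stated derivation rule. With returns matched to dispensing, the average per day is exactly the negative of true use, whatever the number dispensed. This assumes complete return records. Read strictly by visit, the visit counts are wrong in size as well; the figures shown for that reading assume 140 lozenges per dispensing.

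The reach is descriptive: the average in Table 14.3.6.2, the used count and average that Section 7.4 places in the listing, and any compliance decision that relies on the average. Heavy Lozenge Use membership, and its OMI-20 summaries, are affected only if built on this average.

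The primary OMI-20 summary in the mITT population does not use lozenge counts beyond the requirement of at least one lozenge. The day-count compliance rule does not use the average. No inferential result is involved, since Section 6.5 plans none.

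**What to change.** In SAP Section 7.4, replace the sentence that defines the count with:

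*Number of used lozenges = number dispensed at the preceding dispensing visit (Day 0, 7 or 14) minus number returned from that dispensing at the matching return visit (Day 7, 14 or 24).*

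This corrects both the order and the visit reference. The sentence on the average per day can stay as it is. The cost is one sentence, with no new data, no change to the design and no change to any clinical rule.
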